The patients in the intervention group will be mailed a letter about the program in English or Spanish with educational materials about lung screening following randomization and prior to any contact by the PN. A week later, the PN will contact patients over the phone or in person during office visits. For patients that speak languages other than English or Spanish, this initial contact with the PN will be aided by an interpreter. The interpreter will review the recruitment letter and Fact Sheet with the patient and ask the patient if they are interested in continuing with the research study. During this initial contact, the PN will obtain a detailed history to determine if the patient is eligible for lung screening. The PN will educate patients about lung screening and explore their barriers to screening. The PN will coordinate scheduling a shared decision appointment with a provider and, whenever feasible, attend the visit with the patient. The PN will further coordinate scheduling the lung screening test if the provider and patient made that decision and navigate the patient to obtain the test. Interventions may include: reminding the patient about the test, helping with translation, insurance issues, transportation, and overcoming any other system barriers as needed. After screening, PN will review the results. If the patient has an abnormal test result, the navigator will contact the patient's primary care physician and help the patient obtain required follow-up.

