## **V. STUDY PROCEDURE**

### **V.1. Overview**

We propose to develop, implement, and rigorously evaluate a novel lung screening patient navigator program for patients that currently smoke in five community health centers affiliated with a primary care network of a large academic hospital.

Eligible patients will include those receiving care in community health centers who are 55-77 years old and currently smoking. The intervention trial will be randomized at the patient level. In the intervention group, patients will be contacted by a culturally competent PN who will help them stop smoking and obtain lung screening. The control patients will receive usual care. The primary outcome will assess the percentage of eligible patients in intervention and control groups who had at least one chest CT during the study period. Secondary outcomes will include as-treated primary outcomes among intervention patients contacted by the patient navigator, primary outcomes stratified by language spoken, race, age, and practice site, follow-up of abnormal results, percentage of patients with tobacco treatment, and comparison of lung screening to other practices in the primary care network.

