### VI.2 Secondary outcomes

1. Percentage of patients who had at least one chest CT (according to billing and EMR data) during the 1-year study period, comparing patients contacted by patient navigator in the intervention group ("as treated" analysis) vs. all patients in control group.
2. Percentage of patients in intervention vs. control groups who had at least one lung CT screening stratified by language spoken, race, age (<> 65 years) and practice site. (subgroup analysis)
3. Of patients whose initial chest CT generated a radiologist's recommendation for early interval follow-up, the percentage who received the recommended follow-up of in timely manner. The timeliness of care is defined by radiologist's recommendation plus additional 30 days. For recommended biopsy/PET scan we chose 60 days limit. All radiologists at MGH use Lung-RADS system to recommend the follow up post LDCT. These standardized recommendations include 12, 6 or 3 months follow up or for suspicious malignancy PET CT vs biopsy. There is some variability in reading diagnostic chest CT; however recommendations are similar to Lung-RADS. At the end of one-year trial a blinded research assistant will review the electronic medical records of patients who had a chest CT during study period. The dates of imaging will be confirmed by billing data.
4. Mean time to follow-up of abnormal results, comparing intervention and control groups.
5. Tobacco treatment use: Percentage of patients, comparing intervention and control groups, who during the 1-year study period had any of the following:
  - o referral to MA Quitline as determined by patients' QuitWorks data or referral scanned in EHR
  - o smoking cessation medication prescribed in EHR (nicotine patch, gum, lozenge, inhaler, nasal spray or bupropion, or varenicline) during the study period
  - o referral to in-person counseling from CHC-based tobacco coach –documented in EHR
6. Percentage of patients, comparing intervention and control groups, who have a status of former or nonsmoker entered in coded field of EHR at the visit closest to the date of 1 year follow-up.
7. Percentage of patients in intervention group who are reached by PN and percentage of patients reached who had lung screening (process measures)

## AIM 3

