### **VI.3. Analytic Methods**

#### **AIM 2:**

We will examine differences in lung screening rates using chi-square tests.

The comparisons include (1) between intervention and control groups (intention-to-treat analysis), and (2) between patients contacted and not contacted by patient navigators (“as-treated” analysis).

An exploratory subgroup analysis will compare lung screening rates between intervention and control groups stratified by language spoken, race, age (<> 65 years), practice site and other factors.

Furthermore, we will use logistic regression models to examine predictors of lung screening, including patient, provider, and practice characteristics.

In addition to comparing the percentage that completed recommended test in a timely manner between intervention and control group using a chi-square test, we will use survival analysis techniques to compare time to completion between intervention and control groups.

We will also use chi-square tests to compare the percentage with referral to MA Quitline, prescription to smoking cessation medications, referral to in person counseling from CHC tobacco coach, and documented smoking status in EHR between intervention and control groups.

For the intervention group, we will document process measures (percentage reached by PN and percentage agreed to have lung screening test within) and present with 95%CI's.

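### The as-treated secondary analysis has inconsistent comparators, and every version selects on navigator contact, which follows randomisation and occurs only in the intervention arm

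*Combined protocol and SAP*

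**What the plan says.** The as-treated analysis appears in three places.

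- **V.1 Overview** names the group but no comparator: "Secondary outcomes will include as-treated primary outcomes among intervention patients contacted by the patient navigator".
- **VI.2 Secondary outcomes, item 1** gives both sides: "comparing patients contacted by patient navigator in the intervention group", "vs. all patients in control group". Intervention patients who were never reached are in neither group.
- **VI.3, AIM 2** gives the same label to a chi-square "between patients contacted and not contacted by patient navigators". It does not say who makes up the second group.

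No formal rule defines contact. Section IV implies a conversation: "During this initial contact, the PN will obtain a detailed history to determine if the patient is eligible for lung screening". That section also puts randomisation and a mailed letter with educational materials before any navigator contact. V.4 offers controls navigation only after the study year. The outcome in VI.1 is any chest CT in the year. The logistic models in VI.3 are for predictors of screening and are not tied to the as-treated contrast, so as written that contrast is an unadjusted chi-square.

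**The concern.** There are two separate problems.

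First, the comparator is not fixed. On its plain wording, VI.3 places unreached intervention patients in the comparison group, either alone or together with the controls. VI.2 leaves them out. An analyst could follow either statement, and the choice stays open after the data are seen.

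Second, every version selects on something that happens after randomisation and has no counterpart among controls. Reached patients may differ from unreached patients in how likely they are to have a CT anyway. Patients engaged in care may be easier to reach and have more CTs. Sicker patients may be harder to reach and have more diagnostic CTs. The outcome counts any chest CT, and VI.2 item 3 plainly expects diagnostic scans among them: "There is some variability in reading diagnostic chest CT" (a remark there about follow-up recommendations). A non-zero difference could therefore be read as an effect of navigation when it reflects who was reachable.

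**Working it through.** **Inputs from the documents.** Intervention arm 400 (V.4, VI.4). Controls 800 in the V.4 table, or 1276 - 400 = 876 from VI.4. Expected reach: 300 of 400 for one full-time navigator (III), or about 400 with two part-time interpreters/navigators assisting (VI.4). Planned difference 5 points, alpha 0.05, power 88% (VI.4).

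**The plan's own figure.** The 88% is for the primary comparison and cannot be reproduced directly, because no control CT rate is given. With a two-sided pooled test, 88% corresponds to a control rate of 5.3% (400 vs 876) or 5.1% (400 vs 800). Across one- or two-sided tests, pooled or unpooled variance, with or without continuity correction, and either control number, the matching rate runs from 3.5% to 7.3%. I use 5% as an assumption. The 88% is not shown to be wrong, and the point does not depend on it.

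**Assumption the documents cannot supply.** The CT rate q in unreached patients. With no navigator effect and reached share f, the rate in reached patients is r = (base - (1 - f)q)/f.

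**No navigator effect, base 5%, f = 300/400 = 0.75, 800 controls** (simulation, 400,000 runs, uncorrected chi-square). Differences are in percentage points, with the false-positive rate in brackets:

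| q | r | VI.2: contacted vs controls | VI.3 read as contacted vs unreached plus controls | VI.3 read as contacted vs unreached |
|---|---|---|---|---|
| 2% | (5 - 0.5)/0.75 = 6.0% | +1.0 (11.5%) | +1.3 (16%) | +4.0 (31%) |
| 4% | (5 - 1.0)/0.75 = 5.3% | +0.3 (6.1%) | +0.4 (6.5%) | +1.3 (5.4%) |
| 5% | 5.0% | 0 (5.1%) | 0 (4.9%) | 0 (4.4%) |
| 8% | (5 - 2.0)/0.75 = 4.0% | -1.0 (9.3%) | -1.3 (13%) | -4.0 (35%) |

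The unreached-plus-controls rate is (100q + 800 x 5%)/900: 4.67% at q = 2% and 5.33% at q = 8%. The intention-to-treat test stays at about 5% in every row.

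**More patients reached.** At 360 of 400, q = 2% gives r = (5 - 0.2)/0.9 = 5.33%, a difference of +0.3. False positives for the VI.2 version are 5.3-6.1% for q from 2% to 8%. At 400 reached, the VI.2 version is the intention-to-treat comparison and there are no unreached patients to compare with.

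**Other base rates, VI.2 version, 300 reached.** A reached-to-unreached ratio of 3 makes r = 1.2 x base, and a ratio of 0.5 makes r = 0.8 x base, so the difference is ±0.2 x base. At 3.5% that is ±0.7 points (9.6% and 7.4% false positives). At 7.3% it is ±1.5 points (about 14% and 12%).

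**If navigation works as planned.** Suppose it raises the intention-to-treat rate by 5 points, acting only through contact with 75% reached. The effect in reached patients is then 5/0.75 = 6.7 points. In table order, the three contrasts would show:

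- q = 2%: 12.67 - 5.00 = 7.7; 12.67 - 4.67 = 8.0; 12.67 - 2.00 = 10.7.
- q = 8%: 10.67 - 5.00 = 5.7; 10.67 - 5.33 = 5.3; 10.67 - 8.00 = 2.7.

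**Interval for a complier estimate.** For 10% of 400 vs 5% of 800, the half-width is 1.96 x sqrt(0.10 x 0.90/400 + 0.05 x 0.95/800) = 3.3 points. Dividing by 0.75 turns 5 ± 3.3 into 6.7 ± 4.4.

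**The case against.** VI.2 item 1 is a complete definition, and VI.3 may only be summarising it. If not contacted is shorthand for the control arm, who are not offered navigation during the year, the sections agree. That reading is possible, so it goes too far to say that the two statements must give different results. But the text does not say so, and unreached intervention patients are, on plain words, not contacted.

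A reader might infer from the 31-35% error rates or the 10.7-point figure that the plan is badly biased. Those figures belong to a comparison inside the intervention arm, which no section states explicitly. The fully defined VI.2 version is off by about 1 point or less in the base case, against a planned difference of 5.

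A reader might also infer that the as-treated result will exaggerate the benefit. The documents give no CT rate by reachability, and the sign can go either way.

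It is also fair that this is a secondary analysis, labelled as-treated, that intention-to-treat is primary, and that no section calls the result causal. That limits the stakes. It does not remove the need for one comparator and an explicit caveat.

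Finally, a complier-average estimate is no clean substitute. It only rescales the intention-to-treat difference, and it assumes that the mailed materials do nothing. It should not be a required replacement.

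**Conclusion.** The point holds as an inconsistency with a selection problem attached. That VI.2 and VI.3 need to be reconciled, and that contact is a post-randomisation event seen in one arm only, follows from the text without any assumption. The size does not. It rests on an assumed base CT rate, an assumed rate in unreached patients and the share reached. For the VI.2 version the illustration gives an error of at most about 1 point and 5-12% false positives at a 5% base rate with 300 reached. This shrinks towards nothing as reach approaches 400. Readings of VI.3 that include unreached patients can do worse, most of all when they are the whole comparator. The intention-to-treat primary analysis is not affected. The change should be made before analysis, but it does not threaten the trial's main conclusion.

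**What to change.** 1. Delete the contacted vs not-contacted chi-square from VI.3, and use the VI.2 item 1 comparator (contacted intervention patients against all controls) in V.1, VI.2 and VI.3.
2. Define contacted as at least one two-way conversation with the navigator, by phone or in person, recorded during the study year. A letter or an unanswered call does not count.
3. Label the comparison non-randomised and not an estimate of the navigation effect.
4. Optionally, if an effect in reached patients is wanted, add a complier-average estimate: the intention-to-treat risk difference divided by the proportion of the intervention arm reached, with a 95% CI. State its assumption that letters, mailed materials and unanswered calls do not change CT uptake.

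Items 1 to 3 cost wording only, but they leave the selection in place and simply make it visible. Item 4 costs a few lines of code and needs no new data, since the reach percentage is already planned: "we will document process measures (percentage reached by PN". Its price is a wider interval (about 6.7 ± 4.4 against 5 ± 3.3 points at 75% reached) and an assumption that the mailed educational materials strain.

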#### **V.4. Randomized Clinical Trial (Specific Aim 2)**

To test our hypothesis we will randomize eligible patients receiving care at CHCs to one of two study groups:

Early intervention	Usual care/delayed intervention
400 patients will receive 1:1 PN to obtain lung screening and follow-up of abnormal results, as well as smoking cessation guidance	800 patients will receive usual care during the 1-year study period. After the study period they will be offered 1:1 PN to obtain lung screening and follow-up of abnormal results as well as smoking cessation guidance

Eligibility criteria:

1. Inclusion criteria: adult patients aged 55-77 years who are current cigarette smokers (according to an algorithm using EMR data), and receive care at one of the five MGH CHCs.
2. Exclusion criteria: 1) patients who have previously received a diagnosis of lung cancer per EMR, 2) have undergone a chest CT within 18 months before enrollment, 3) are subsequently identified as having died prior to the study intervention 4) deemed by their primary care provider as not eligible for lung screening

Patients will be identified using existing electronic systems developed by the MGH Primary Care Operations Improvement (PCOI) program (Protocol # 2004P002796).

Using a newly developed TopCare smoking and lung screening registry, we will identify smokers receiving care at MGH health centers who could be eligible for lung screening. We will e-mail primary care providers a list of their patients and ask them to notify us in a week if they do not want us to contact a patient and to provide a reason why they believe patient is not eligible for lung screening. The eligible patients will then be randomly allocated to the intervention or usual care groups. Patients randomly assigned to the intervention group will be eligible for PN, while patients randomly assigned to the control will receive usual care and be eligible for navigation after the one year period.

Patient navigator intervention:

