### **VI.4. Sample Size Calculations**

We hypothesize that the navigator program will increase lung screening in the intervention group by at least 5%. With a total sample size of 1276 smokers, 400 randomized to the intervention group, and an alpha level of 0.05, we will have 88% power to detect a 5% difference. From our prior experience, a full time navigator with the assistance of two part-time interpreters/navigators can reach about 400 patients over nine months. Since our intervention includes follow-up of abnormal results, our study will last 1-year.

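### The exploratory subgroup analysis compares arms within strata with no test of whether the effect differs between them, so differences in stratum significance may be misread as unequal benefit

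*Combined protocol and SAP*

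**What the plan says.** Section VI.3 (AIM 2) names chi-square tests for differences in lung screening rates. It then adds: "An exploratory subgroup analysis will compare lung screening rates between intervention and control groups stratified by language spoken", together with race, age, practice site and an unspecified set of other factors. The same section plans logistic regression for predictors of screening, using patient, provider and practice characteristics. It mentions no product term between treatment arm and a subgroup factor. No test of heterogeneity, multiplicity rule or rule for interpreting subgroups appears anywhere.

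The status and endpoint of this analysis vary between sections:

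- Section VI.3 calls it exploratory and speaks of lung screening rates, the same term that it uses for the intention-to-treat comparison.
- Section VI.2 lists it as secondary outcome 2, with the endpoint "at least one lung CT screening stratified by language spoken, race, age (<> 65 years) and practice site".
- Section V.1 lists it among the secondary outcomes as "primary outcomes stratified by language spoken, race, age, and practice site".
- Section VI.1 defines the primary outcome as at least one chest CT during the study year.

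The only effect hypothesis, in section VI.4, is an overall gain of at least 5%. No difference in effect between subgroups is hypothesised.

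**The concern.** A comparison of arms inside one stratum asks whether navigation works there. It does not ask whether navigation works differently there than elsewhere. That second question needs a direct comparison of the stratum effects. Significance at one health center and not at another is not evidence of a difference, least of all when each center has only a fraction of the sample.

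Section VIII says that resources may be expanded if the intervention proves effective. A center or language group that appears not to benefit, purely by chance, could influence where that happens. The open category of other factors gives further room for chance patterns.

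The endpoint wording matters for a separate reason. Section VI.2, item 3, itself distinguishes LDCT from diagnostic chest CT. If the subgroups counted only screening CTs while the primary analysis counted any chest CT, the subgroup effects could not be set beside the overall effect.

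**Working it through.** **Inputs from the documents**

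- Section VI.4: "With a total sample size of 1276 smokers, 400 randomized to the intervention group", which leaves 1276 − 400 = 876 controls; also "an alpha level of 0.05" and "we will have 88% power to detect a 5% difference".
- Section V.4: "800 patients will receive usual care during the 1-year study period", against 400 navigated. The two control totals differ, so both are used.
- Five health centers (section V.4).

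**Assumptions, because the documents do not give them**

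- Two-sided testing, and 5% read as 5 percentage points.
- A control rate of 5%, varied from 4% to 10%.
- Equal strata: 80 vs 160 (or about 175) per center, and 200 vs 400 (or 438) per age half.
- The same true gain of 5 points in every stratum.

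**Step 1. The plan's own power figure.** With p̄ the pooled proportion, SE₀ = √[p̄(1−p̄)(1/n₁+1/n₂)] and SE₁ = √[p₁(1−p₁)/n₁ + p₂(1−p₂)/n₂],

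power = Φ[(|p₁−p₂| − 1.96·SE₀)/SE₁].

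For 10% vs 5% with 400 vs 876: p̄ = 83.8/1276 = 0.0657, SE₀ = 0.01495, SE₁ = 0.01671. Power = Φ[(0.05 − 0.0293)/0.01671] = Φ(1.24) = 89.2%. With 800 controls it is 88.3%. The stated 88% cannot be derived from the documents, because no control rate is given, but it is compatible with 5%. This supports 5% as the central assumption and does no more than that.

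**Step 2. One health center, 80 vs 160, 10% vs 5%.** SE₀ = 0.03416 and SE₁ = 0.03771, so power = Φ[(0.05 − 0.0670)/0.03771] = Φ(−0.45) = 32.7%. Expected counts are 8 patients with a CT in each arm.

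**Step 3. Chance of a mix of significant and non-significant centers.** 1 − 0.327⁵ − 0.673⁵ = 1 − 0.004 − 0.138 = 0.858.

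**Step 4. Two age halves, 200 vs 400.** SE₀ = 0.02160 and SE₁ = 0.02385, so power = Φ(0.32) = 62.6%. The chance that the halves disagree is 2 × 0.626 × 0.374 = 0.468.

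**Step 5. Range.** In each cell the first figure uses 800 controls and the second 876.

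| Control rate | Power per center | Mixed over 5 centers | Power per half | Halves disagree |
|---|---|---|---|---|
| 4% | 37% / 38% | 89% / 90% | 68% / 70% | 43% / 42% |
| 5% | 33% / 34% | 86% / 87% | 63% / 64% | 47% / 46% |
| 6% | 29% / 31% | 82% / 84% | 58% / 59% | 49% / 48% |
| 8% | 25% / 26% | 76% / 77% | 50% / 51% | 50% / 50% |
| 10% | 22% / 23% | 71% / 72% | 44% / 45% | 49% / 50% |

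**Step 6. The alternative.** A simulation of 100,000 trials per setting (876 controls, uniform effect) applied one interaction test per factor. It falsely signalled unequal benefit in about 2% to 5% of trials. In the same simulation, at least one of the five centers showed no benefit or an apparent harm in 37% of trials at a 5% control rate and 41% at 6%. Point estimates alone can therefore also mislead.

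**Step 7. What an interaction test can detect.** Take two halves of 200 vs 438, a control rate of 6%, and the risk-difference scale. For true gains of 7.5 and 2.5 points, the standard error of the difference is 0.0351 and power is Φ(0.05/0.0351 − 1.96) = Φ(−0.53) = 30%. For 10 and 0 points, the standard error is 0.0348 and power is Φ(0.10/0.0348 − 1.96) = Φ(0.91) = 82%.

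**The case against.** The strongest reply is that the plan calls this analysis exploratory, and that nothing in it says strata will be contrasted by their p-values or that unequal benefit will be concluded. Both points stand. A reader might infer that the plan will declare unequal benefit, but the documents support only a risk of misreading. Even the chi-square test within each stratum is inferred from the general sentence that opens the AIM 2 methods. It is the natural inference, since no other test is named for comparing these rates. The exploratory label lowers the weight of the results but does not supply the missing comparison, and sections V.1 and VI.2 list the analysis among the secondary outcomes.

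A reader might also infer that the subgroups use a different endpoint from the primary. Only item 2 of section VI.2 suggests this. Section V.1 says the subgroups use the primary outcomes, and section VI.3 uses one term for both analyses. Aim 3 shows the same loose usage, with a chest CT outcome and a test on lung screening rates. The supportable point is inconsistent wording.

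Nor are language, race and site the equity question as the trial defines it. Specific Aim 3 defines equity as health center patients against patients of other practices in the network.

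Finally, the figures rest on an assumed control rate and equal strata, and nothing is computed for language or race. That is correct and limits the precision. The range over control rates does not remove the problem, and unequal strata would have lower power in the smaller groups.

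**Conclusion.** The point holds as a fault in an exploratory analysis. As written, the analysis has no means of telling a real difference in effect from chance. Under a uniform gain of 5 points and equal strata, five separate center tests give mixed results in about 71% to 90% of trials for control rates of 10% to 4% (about 86% at 5%), and two age halves disagree in about 42% to 50%. It would go too far to say that mixed verdicts are nearly certain for every factor: for age they arise in half of trials or fewer. The endpoint wording needs reconciling but does not establish a second endpoint. The primary comparison is unaffected. The change should be made before the analysis, since it alters the method and costs almost nothing.

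**What to change.** 1. Name the primary endpoint, any chest CT in the study year, as the endpoint of the subgroup analysis, and make sections V.1, VI.2 and VI.3 agree.
2. Close the factor list at language, race, age (<65, ≥65) and site, and remove the open category. The current age notation does not place patients aged exactly 65.
3. For each factor, fit a model with treatment arm, the factor and their interaction. This is an addition: the planned logistic models of predictors do not mention treatment arm.
4. Report one interaction p-value per factor, with stratum risk differences and 95% confidence intervals, in place of within-stratum p-values. Put the test and the displayed effects on the same scale. When control rates differ between strata, a uniform risk difference is not a uniform odds ratio, so an odds-ratio interaction test may not match a table of risk differences.
5. State that a non-significant interaction is not proof of equal benefit. Power is low for moderate differences (30% for gains of 7.5 against 2.5 points in two halves), and the intervals should carry the interpretation.

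The cost is a few lines of text and a little more analysis work, with no new data.

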### **III. SUBJECT SELECTION**

According to internal MGH data from 2012, 1480 patients aged 55-79 years at MGH CHCs were current smokers. Of these patients, 204 had a chest CT scan in the prior 18-months and/or had a diagnosis of lung cancer. Because of new Medicare guidelines we will only include patients that are aged 55-77 years and additionally exclude patients that providers deem ineligible for lung cancer screening. We estimate the total number of patients eligible for our interventions to be around 1200. Our experience in prior PN colorectal cancer screening interventions is that one full-time navigator assigned 400 patients will be able to reach/work with 300 patients over a 9-month period. Since our navigator will also follow-up abnormal CT results, our study will last one year. Eligible patients will be identified, randomized, and an electronic list of patients will be downloaded into an existing TopCare navigator data base. The navigators will use this system to track patients and interventions. Patients randomized to the interventions group will be recruited by navigators during their visits to the health center or over the phone. Since the navigator program is already standard of care at MGH, its expansion to include lung screening is considered part of usual care.

For Specific Aim 5, primary care physicians (PCPs) and nurse practitioners (NPs) from the community health centers with the PN program will be asked to complete a survey following the study period. There are approximately 81 PCPs and NPs who will be asked to complete the survey.

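### The logistic models of screening predictors name no method for correlation within provider or health center, so as written their provider-level and practice-level standard errors would be too small

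*Combined protocol and SAP*

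**What the plan says.** Section VI.3 (Aim 2) first plans chi-square tests between arms and an exploratory subgroup analysis. It then adds a modeling step: "we will use logistic regression models to examine predictors of lung screening, including patient, provider, and practice characteristics". It names no random effect, GEE or robust variance, and no other section mentions clustering or an ICC.

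The data structure has to be assembled from other sections:

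- **Patients.** Section III says "We estimate the total number of patients eligible for our interventions to be around 1200". The design table in V.4 agrees, with 400 early-intervention patients and "800 patients will receive usual care during the 1-year study period". Section VI.4 uses a larger figure: "With a total sample size of 1276 smokers, 400 randomized to the intervention group, and an alpha level of 0.05".
- **Providers.** Section III, on the Aim 5 survey: "There are approximately 81 PCPs and NPs who will be asked to complete the survey".
- **Sites.** Section V.1 places the program "in five community health centers affiliated with a primary care network of a large academic hospital".
- **Unit of randomization.** Section V.1: "The intervention trial will be randomized at the patient level".

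**The concern.** A provider characteristic takes at most about 81 independent values in this trial, and a practice characteristic at most five. Ordinary logistic regression computes its standard errors as if each of the roughly 1200 patients brought independent information on both. If patients of one provider, or of one center, resemble each other in whether they get a chest CT, the reported precision for those coefficients is too high.

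Some correlation is plausible from the protocol itself. Section II notes that Medicare requires a written order and a shared decision-making visit with a practitioner. Under V.4 the navigator arranges the scan only after provider and patient have decided on it, and providers remove from their own lists patients they judge ineligible. Looking for provider predictors also presumes that providers differ.

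Randomizing patients protects the arm comparison. It does nothing for provider and practice characteristics, which are not randomized. At stake are the intervals and p-values attached to any reported provider or practice predictor of screening.

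**Working it through.** **1. The plan's own figure.** The documents state no figure for the logistic models. The only related one is 88% power for the arm comparison (VI.4). It cannot be rebuilt from the documents alone, because no control rate is given. Assuming 5% versus 10%, two-sided pooled power is 89.2% with 400 versus 876 patients (1276 − 400 = 876) and 88.3% with 400 versus 800. Both are close to 88%. At a 10% control rate and 1276 patients it would be 72.3%.

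**2. Inputs for the predictor models.** Patients: 1200 (III, V.4) or 1276 (VI.4). Providers: about 81 (III). Sites: 5 (V.1). ICC: not given, so assumed and varied.

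**3. Formulas.** With average cluster size m, the design effect for a cluster-level predictor is DE = 1 + (m − 1) × ICC, with the ICC on the observed (0/1) scale. The ordinary standard error is too small by a factor √DE. Actual two-sided type I error at nominal 5% is 2 × [1 − Φ(1.96/√DE)].

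**4. Provider level.** m = 1276/81 = 15.8.

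| Assumed ICC | DE | √DE | Type I error |
|---|---|---|---|
| 0 | 1.00 | 1.00 | 5.0% |
| 0.01 | 1.15 | 1.07 | 6.7% |
| 0.05 | 1.74 | 1.32 | 13.7% |
| 0.10 | 2.48 | 1.57 | 21.3% |

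With 1200 patients (m = 14.8) the type I errors at ICC 0.01, 0.05 and 0.10 are 6.6%, 13.2% and 20.4%.

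**5. Practice level.** m = 1200/5 = 240.

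| Assumed ICC | DE | √DE | Type I error |
|---|---|---|---|
| 0.001 | 1.24 | 1.11 | 7.8% |
| 0.01 | 3.39 | 1.84 | 28.7% |
| 0.02 | 5.78 | 2.40 | 41.5% |
| 0.05 | 12.95 | 3.60 | 58.6% |

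With 1276 patients (m = 255.2) the value at ICC 0.01 is 29.8%.

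**6. Check by simulation.** Ordinary logistic regression was fitted to 800 simulated trials, each with 1200 patients, 400 of them randomized to intervention, 81 providers in five sites, and about 10% screening in controls (assumed). The ICCs here are on the latent scale. The ratio is the true standard deviation of the coefficient over the mean model standard error.

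| Latent ICC, provider / site | Provider predictor: ratio, type I error | Practice predictor: ratio, type I error | Randomized arm: ratio, type I error |
|---|---|---|---|
| 0 / 0 | 1.01, 5% | 1.02, 6% | 1.01, 6% |
| 0.05 / 0.02 | 1.14, 8% | 1.59, 21% | 1.01, 6% |
| 0.10 / 0.02 | 1.29, 13% | 1.84, 29% | 1.03, 6% |

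Simulation error at a true 5% is √(0.05 × 0.95/800) = 0.8 points, so the arm results are consistent with the nominal level. A patient-level predictor behaved the same way (ratio 1.02 to 1.05, type I error 5% to 6%).

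**7. Reconciling the two scales.** At 10% screening, the observed-scale ICC is roughly p(1 − p) times the between-cluster variance on the logit scale. For the second row of the simulation the provider value is 0.09 × 0.42² = 0.016 and the site value is 0.09 × 0.26² = 0.006. With 1200 patients the formula in step 3 then gives 7.6% at provider level and 20.9% at site level, in line with the simulated 8% and 21%.

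**8. Would clustering on provider be enough?** For provider predictors, nearly: provider-robust standard errors brought type I error to 5% to 6% in the two clustered rows. For practice predictors, no: it was still 16% in the second row and 20% in the third (19.5%).

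**The case against.** The strongest reply is that the plan is silent rather than wrong. Logistic regression does not exclude GEE or a random intercept, and VI.3 nowhere says that patients will be treated as independent. That is fair as a reading of the words, and it is why the point is conditional on the models being fitted as written. It does not dispose of the point: the method as named gives wrong error bars for two of the three kinds of predictor it lists, and nothing elsewhere corrects it.

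Second, the analysis is peripheral. These models appear in neither the primary outcome (VI.1) nor the seven secondary outcomes (VI.2), and no significance threshold is set for them. That stands, and it limits the importance of the point.

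Third, every inflation figure rests on an assumed ICC and on a provider count taken from a survey. That also stands. The direction holds for any positive ICC; the size is not known.

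A reader might go further in three ways that the documents do not support.

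- **That the primary result or its power is undermined.** Patients are randomized individually, and the simulated arm effect kept its nominal error rate.
- **That false positives would be far above 5% throughout.** At a provider ICC of 0.01 the figure is 6.7%. Values near 59% need an observed-scale site ICC of 0.05, for which the documents give no basis.
- **That these predictors would decide who receives navigation.** Section VIII ties wider use to the intervention being effective, and V.4 offers navigation to the whole control group after the study year.

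**Conclusion.** The point holds for provider-level and practice-level coefficients only. The size depends on the ICC, the scale on which it is expressed, and roughly equal cluster sizes. On the observed scale, a provider-level predictor tested at nominal 5% would have a type I error of about 7% to 21% for ICC 0.01 to 0.10. For a practice-level predictor it would be about 29% at ICC 0.01, and higher with a larger ICC. At ICC zero there is no problem.

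The practice level has a second difficulty that no standard error repairs. With five sites, a practice characteristic cannot be separated from everything else that distinguishes those sites. The matter is worth correcting because it is cheap to do so, but it concerns a supportive analysis and does not bear on the trial's main conclusion.

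**What to change.** In VI.3 (Aim 2), state that:

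- the predictor models will be fitted by GEE with robust standard errors clustered on provider, or as logistic models with a provider random intercept;
- the five health centers will enter as fixed effects;
- practice-level differences will be reported descriptively, as screening rates by center, without formal tests of practice characteristics;
- the number of providers to whom trial patients are attributed will be reported, since the 81 is a survey count.

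The cost is wider intervals for provider predictors and the loss of a formal test of practice characteristics, which is part of what the plan now intends. No further patients or outcome data are needed, and the primary chi-square test and the sample size stay as they are.
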